## 11.2 Partial Date Conventions

### Algorithms for Adverse Events, Medical History, and Prior and Concomitant Medications

Partial date to be imputed as:

Start Date	Stop Date	Action
Complete	Complete	No action
Partial, but known components shows it can't be on or after study medication start	Complete	Impute the start date as "01", if only the day is missing. Impute the start date as "01 January", if month and day are missing.
	Date and/or month missing	Impute the stop date as the latest possible date (i.e., last day of the month, if only the day is missing or "31 December" if month and day are missing).
Partial, could be on or after the study medication start  Or  missing	Complete	

1) If stop date < study medication start then, Impute the start date as earliest possible date (i.e., "01", if only the day is missing or "01 January", if month and day are missing).

2) If stop date <math>\geq</math> study medication start then, impute the start date equal to the study medication start date.

	Partial	Impute the stop date as the latest possible date (i.e., last day of the month, if only the day is missing or "31 December" if month and day are missing). then, 

1) If stop date < study medication start then, impute the start date earliest possible date.

2) If stop date <math>\geq</math> study medication start, then impute the start date equal to the study medication start date.

	Missing	Missing date will not be imputed.

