**Treatment-emergent AEs (TEAEs)** are AEs that developed or worsened in severity compared to the baseline during the treatment and follow-up period (including the extended follow-up). As only the worsening pre-existing AEs and new AEs reported during the treatment and follow-up period (including the extended follow-up) will be collected in the study, all AEs collected

during the treatment and follow-up period (including the extended follow-up) are considered as TEAEs.

**TEAE that are infusion related reaction** will be summarized. Localized injection/infusion reactions that may include pruritus, pain, erythema, swelling, rashes, or bleeding around the injection/infusion site. Systemic injection/infusion-related reactions may be immediate type or delayed type immune complex-associated hypersensitivity reactions (e.g., serum sickness).

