#### 5.7.2.2 *Responder type (binary) efficacy endpoints*

The responder type (binary) endpoints will be reported using frequency and percentage by treatment along with the 95% Clopper-Pearson exact confidence interval for the proportion.

Based on the estimand framework introduced in [ICH E9\(R1\)](#), additional details relating to the definition of the estimand is proposed.

Handling of intercurrent events (for responder type binary endpoints) of treatment discontinuation and prohibited medication:

- *Treatment discontinuation*: Treatment policy strategy will be followed. i.e., all the collected data available after treatment discontinuation will be included in the analysis.
- *Any prohibited medication*: Participant will be reported as non-responder at all the visits occurring after the prohibited medication start.

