### **5.8.1 Analysis of Adverse Events**

Incidence tables for both non-TEAEs and TEAEs will be presented for each treatment group and collectively for the combined IMG-007 group. TEAEs will be classified into two groups as follows:

- TEAEs occurred through the 24 weeks of study period: TEAEs with the starting date between the date of first treatment administration and week 24 visit (or end of study, if achieved prior to week 24 visit) will be considered here.
- TEAEs occurring through the 36 weeks of study period: TEAEs with starting between the date of first treatment administration and week 36 visit (or end of study, if achieved prior to week 36 visit) will be considered here.

The table will include the number (n) and percentage (%) of participants who are experiencing an adverse event, along with the corresponding number of episodes of AEs. Participants with multiple adverse events in a particular category will be counted only once in that category.

Participants with multiple severities/grading will be counted only once under maximum severity/grading.

The number and proportion of participants reporting non-TEAEs/TEAEs will be summarized, sorted by decreasing frequency of SOC and PT in the combined IMG-007 group, and in case of ties, then sorted by decreasing frequency of SOC and PT in the IMG-007 [REDACTED] group, and finally, in case of further ties, then alphabetically.

Listings will be provided by SOC and PT, for non-TEAEs, TEAEs and TESAEs, TEAEs of infusion related reactions, and TEAEs leading to study treatment discontinuation.

The following summaries will be provided for the adverse events by treatment group.

- Overall summary of AEs during the 24-Week Period: The overall summary of AEs will be provided with number and proportions of participants with any:
  - non-TEAE
  - TEAE
  - Related TEAE
  - SAE
  - TEAE by CTCAE grades
  - TEAE that are infusion related reaction
  - TEAE leading to 4-week dosing period discontinuation
  - TEAE leading to 16-week dosing period discontinuation
  - TEAE leading to study discontinuation
  - TEAE with outcome of death
- Overall summary of AEs during the 36 weeks of study period: The overall summary of AEs will be provided with number and proportions of participants with any:
  - TEAE
  - Related TEAE
  - SAE
  - TEAE by CTCAE grades
  - TEAE leading to study discontinuation
  - TEAE with outcome of death
- Summary of non-TEAEs by SOC and PT
- Summary of TEAEs by SOC and PT during 24-Week period

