## 5.10 Analysis of Pharmacodynamic Data

### 5.10.1 Handling of PD data based on the prohibited medication use

All the PD assessments (except OX40 occupancy on CD4+ T cell and OX40+/CD4+ T cell in CD4+ T cell) will be treated similar to the secondary efficacy assessment for handling the intercurrent event (prohibited medication). That is, all PD assessments after the start date of first prohibited medication use of each participant will be set to missing. The results for OX40 occupancy on CD4+ T cells and OX40+/CD4+ T cells within CD4+ T cells will be used as collected.

Statistical analysis of the following pharmacodynamic variables will be presented.

- Listing of RO (%) by visit for individual
- Table and figure of RO (%) over time for each dose group
- Listing of Percentage of OX40+/CD4+ T cell in CD4+ T cell (%) by visit for individual
- Table and figure of Percentage of OX40+/CD4+ T cell in CD4+ T cell over time for each dose group
- Listing of Olink target 48 cytokine panel proteins levels in serum (pg/mL), by visit for individual (45 proteins)
- Table and figure of Olink target 48 cytokine panel proteins levels in serum (pg/mL) log10 transformed change from baseline over time for each dose group (45 proteins)
- Listing of Olink target 48 immune surveillance panel proteins levels in serum (pg/mL), by visit for individual (44 proteins)
- Table and figure of Olink target 48 immune surveillance panel proteins levels in serum (pg/mL) log10 transformed change from baseline over time for each dose group (44 proteins)
- Figure of baseline Th1/Th2/Th17/Th22 fold change vs healthy subject for individual
- Figure of baseline, Week 16 and Week 24 Th1/Th2/Th17/Th22 fold change vs healthy subject for each dose group
- Table and figure of IgE (IU/mL) log10 transformed change from baseline over time for each dose group
- Listing of levels of IgE for individual
- Listing of OX40 positive cells (cells/mm^2) in biopsy by visit for individual
- Table and figure of Week 24 LS (Lesion) vs Week 16 LS vs baseline LS vs baseline NL (non-lesion) OX40 positive cells in biopsy for each dose group
- Listing of OX40L positive cells (cells/mm^2) in biopsy by visit for individual
- Table and figure of Week 24 LS vs Week 16 LS vs baseline LS vs baseline NL OX40L positive cells in biopsy for each dose group
- Listing of Tryptase positive cells (cells/mm^2) in biopsy by visit for individual

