### *Adverse event*

If the intensity of a TEAE is missing, it will be classified as “severe” in the frequency tables by intensity of TEAE. If the assessment of relationship of a TEAE to the investigational product is missing, it will be classified as “related” in the frequency tables by relation to the investigational product.

The partial date values will be imputed as specified in the [Appendix 11.2](#). Imputed dates will not be presented in the listings.

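### SAP Appendix 11.2 has no row for a partial start date known to fall after first dose; read literally, it resets that start to the first-dose date

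*SAP*

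**What the plan says.** The heading of the table in SAP Appendix 11.2 covers adverse events, medical history, and prior and concomitant medications. Apart from complete dates, it has two classes of start date.

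- **Known components place the start before first dose.** The start goes to the first of the month, or to 1 January if the month is also missing.
- **"Partial, could be on or after the study medication start"**, which also takes wholly missing starts. If the stop date (moved to its latest possible date when partial) precedes first dose, the start takes its earliest possible date. If the stop is on or after first dose, the instruction is to "impute the start date equal to the study medication start date". If the stop is missing, the only text is "Missing date will not be imputed".

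SAP 6.2 applies the table to adverse events: "The partial date values will be imputed as specified in the" appendix. The only other partial-date rule, in SAP 4.1, concerns AA diagnosis and current-episode dates.

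Three analyses depend on a start date that may be partial:

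- SAP 5.8.1 builds its 24-week tables from "TEAEs with the starting date between the date of first treatment administration and week 24 visit".
- SAP 5.7.2.2, on prohibited medication: "Participant will be reported as non-responder at all the visits occurring after the prohibited medication start".
- SAP 5.10.1: "all PD assessments after the start date of first prohibited medication use of each participant will be set to missing", with two OX40 T-cell measures exempt.

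**The concern.** Using the first-dose date is a sensible default when the known components include the dosing month or year, because it protects treatment-emergent status. When the recorded month or year is already later than first dose, there is nothing to protect. Under SAP 4.6.1, TEAEs "are AEs that developed or worsened in severity compared to the baseline during the treatment and follow-up period", so the event qualifies on either date. The imputation then only contradicts recorded data.

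Two sets of results could be affected. First, the 24-week TEAE tables would include events known to have begun after Week 24. The by-term summaries of Grade 3 or higher events, events leading to treatment discontinuation, and deaths are listed for 24 weeks only, so no 36-week counterpart would reveal the shift. Imputed dates are also kept out of the listings (SAP 6.2), so a reader could not see why table and listing disagree. Second, if imputed dates are used for prohibited medications, one started late is dated Day 1. The participant is then a SALT30 non-responder at every post-baseline visit and loses most post-baseline PD data.

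**Working it through.** **Does the table ever keep a known later month or year?** The two partial classes are complements: 'cannot be' and 'could be' on or after first dose. A start that must be after first dose is not in the first, so it falls in the second. Its stop cannot precede first dose, so the branch that keeps known components cannot be reached. As a check, the table was coded as written and run for every first-dose date from 1 July 2023 to 30 June 2024. The starts were month-and-year or year-only dates lying wholly after first dose and no later than Day 253. Each was paired with a complete, a month-only and a year-only stop. All 9,831 of 9,831 combinations were set to the first-dose date, 1 to 252 days before the earliest date the known components allow.

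**Worked example.** Assume first dose on 1 March 2024, a start recorded as September 2024 with the day unknown, and a stop on 20 September 2024. Study day = date − first-dose date + 1.

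- 1 September 2024 is Day 185 and 20 September is Day 204, so true onset is Day 185 to 204.
- Week 24 (Day 169) is 16 August 2024, so the event began after Week 24.
- The table imputes Day 1. Keeping the month gives Day 185.

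**Adverse events.** First-dose dates: every day in 2023 and 2024 (365 + 366 = 731). True onset: each day from 170 to 253 (84 days). Cases: 731 × 84 = 61,404, each with a stop on or after onset. An event enters the 24-week table if its imputed start is no later than Day 169.

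| Known part of start | Rule | In 24-week table |
|---|---|---|
| Month and year | As written | 61,404 / 61,404 = 100% |
| Month and year | Keep the month | 10,774 / 61,404 = 17.5% |
| Year only | Earliest consistent date | 88.4% |

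Under the keep-the-month rule the latest true onset still counted is Day 199: the first of a 31-day month falls on Day 169, and 169 + 30 = 199.

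**Prohibited medications, if imputed dates are used.** SALT visits from SAP Appendix 11.3, Group 5: Days 29, 43, 57, 85, 113, 141, 169, 211 and 253, nine in all. Wrongly failed visits = (visits after imputed start) − (visits after true start).

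- Example dates: 9 − 2 = 7 visits wrongly failed, since only Weeks 30 and 36 follow the true start. With the month kept, 2 − 2 = 0.
- All true starts from Day 2 to 253 in a month later than the dosing month (173,438 cases):

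| Rule | Mean wrongly failed, all 9 visits | Mean wrongly failed, 7 visits to Week 24 |
|---|---|---|
| As written | 4.99 | 4.81 |
| Keep the month | 0.50 | 0.43 |

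One participant wrongly failed at a visit lowers SALT30 there by 1/6 = 16.7 points in Cohort 1 or 1/24 = 4.2 points in Cohort 2, if that participant was otherwise a responder.

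**The case against.** The strongest reply is that little of weight moves. TEAE status is untouched. So is 36-week incidence for records with a stop date. Overall 24-week incidence changes only if the participant had no other TEAE by Week 24; otherwise a SOC/PT row or an episode count changes. There is no control arm, so no treatment contrast is distorted. The error runs against the drug for adverse events and SALT30, in line with SAP 6.2, which calls missing severity severe and missing relationship related. With about 30 participants, dates collected for every event and queries raised on discrepancies, such records may be few or absent. All of this stands and limits the importance of the point. It does not justify the rule: a conservative default is meant for missing information, and here the information was recorded.

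The medication effect is also conditional. SAP 6.2 invokes the table expressly only for adverse events, and neither 5.7.2.2 nor 5.10.1 says that imputed dates are used. That is correct, but the appendix heading includes concomitant medications, so the SAP should settle it. Any loss of secondary SALT data is only an inference from 5.10.1, which says PD is handled like the secondary efficacy assessment; the public text of 5.7.1 does not show that rule. No weight is placed on it here.

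Finally, 'could be' might mean 'uncertain only'. The table would then not override known dates, but those dates would have no row at all and the programmer would have to invent one.

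For year-only starts the gain is small. In 42.4% of the enumerated cases onset is in the first-dose year and the proposed rule still gives Day 1. Among later-year cases, 79.8% still enter the 24-week table.

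**Conclusion.** The concern holds. On the literal reading, a partial start known to be after first dose is moved to first dose whenever a complete or partial stop date exists. On the narrower reading it has no rule. When the stop is missing, it is unclear whether the partial start is imputed. No other section repairs this.

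The fault should be corrected, but it does not threaten the primary conclusion. For day-missing adverse events, the rule puts every onset after Week 24 into the 24-week tables where about one in six would remain under a better rule. For prohibited medications the cost is about 4.5 extra SALT30 visits wrongly failed per affected participant (4.99 − 0.50), if imputed dates are used at all.

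These figures are per affected record. They assume uniform onset and take Day 169 as the Week 24 visit, whereas SAP 5.8.1 uses the actual visit, which has a 3-day window either side. The documents do not say how many partial dates there are.

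**What to change.** Amend SAP Appendix 11.2 before database lock:

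1. Add a row: if the known month or year is later than that of first dose, impute the earliest date consistent with the known components (the first of the month, or 1 January if only a later year is known).
2. Limit the first-dose date to starts whose known components include it, or that are wholly missing, where the stop does not precede first dose.
3. Apply the same start rule when the stop is missing or the event is ongoing.
4. State whether imputed medication dates drive the prohibited-medication rules in SAP 5.7.2.2 and 5.10.1.

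The cost is one table row, a sentence or two and a few lines of code. Some onsets after Week 24 will still fall in the 24-week tables: 17.5% of Day 170 to 253 onsets when only the day is missing, and about 88% when only the year is known. Year-only dates should therefore be queried with the site.

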### 11.3 Analysis Visit Window

Analysis Visit	Target Day	Group 1	Group 2	Group 3	Group 4	Group 5*	Group 6	Group 7
Baseline	1	Up to day 1	Up to day 1	Up to day 1	Up to day 1	Up to day 1	Up to day 1	Up to day 1
Week 1	8	2-11	-	-	-	-	-	-
Week 2**	15	12-25	2-25	2-25	2-25	-	-	2-25
Week 4	29	26-36	26-36	26-71	26-43	2-36	-	>25
Week 6	43	37-50	37-50	-	-	37-50	-	-
Week 8	57	51-71	51-71	-	44-71	51-71	-	-
Week 12	85	72-99	72-99	-	72-99	72-99	-	-
Week 16	113	100-127	100-127	72-141	100-127	100-127	2-141	-
Week 20	141	128-155	128-155	-	128-155	128-155	-	-
Week 24	169	156-190	156-190	142-211	156-211	156-190	142-190	-
Week 30	211	191-232	-	-	-	191-232	191-232	-
Week 36	253	233-274	-	212-274	212-274	233-274	233-274	-

Group 1: Vital signs, Physical examination, Adverse events, Prior and concomitant therapies, Hematology, blood chemistry, PK sampling.

Group 2: ADA sampling

Group 3: Urinalysis

Group 4: Pregnancy test

Group 5: SALT, IATS, IGA-EB, IGA-EL, IGA-FN, PGIS-AA, PGIS-S, PGIS-EB, PGIS-EL, PGIS-FN, AAPPO, HADS

Group 6: ECG, TB testing and TB risk follow up

Group 7: Study treatment administration

\*Use group 5 for PD blood sample by removing week 6 and changing the Week 4 window from “2-36” to “2-43” and Week 8 window from ’51-71’ to “44-71”.

\*\* The upper bound of window period extended by 3 days to accommodate the unscheduled Week 2 assessments.

## 11.4 CTCAE Version 5.0 for Key Hematology and Serum Chemistry Parameters

CTCAE Term	Grade 1	Grade 2	Grade 3	Grade 4	Grade 5
White blood cell decreased	<LLN - 3000/mm3; <LLN - 3.0 x 10e9 /L	<3000 - 2000/mm3; <3.0 - 2.0 x 10e9 /L	<2000 - 1000/mm3; <2.0 - 1.0 x 10e9 /L	<1000/mm3; <1.0 x 10e9 /L	-
Neutrophil count decreased	<LLN - 1500/mm3; <LLN - 1.5 x 10e9 /L	<1500 - 1000/mm3; <1.5 - 1.0 x 10e9 /L	<1000 - 500/mm3; <1.0 - 0.5 x 10e9 /L	<500/mm3; <0.5 x 10e9 /L	-
Lymphocyte count decreased	<LLN - 800/mm3; <LLN - 0.8 x 10e9/L	<800 - 500/mm3; <0.8 - 0.5 x 10e9 /L	<500 - 200/mm3; <0.5 - 0.2 x 10e9 /L	<200/mm3; <0.2 x 10e9 /L	-
Anemia	Hemoglobin (Hgb) <LLN - 10.0 g/dL; <LLN - 6.2 mmol/L; <LLN - 100 g/L	Hgb <10.0 - 8.0 g/dL; <6.2 - 4.9 mmol/L; <100 - 80g/L	Hgb <8.0 g/dL; <4.9 mmol/L; <80 g/L; transfusion indicated	Life-threatening consequences; urgent intervention indicated	Death
Platelet count decreased	<LLN - 75,000/mm3; <LLN - 75.0 x 10e9 /L	<75,000 - 50,000/mm3; <75.0 - 50.0 x 10e9 /L	<50,000 - 25,000/mm3; <50.0 - 25.0 x 10e9 /L	<25,000/mm3; <25.0 x 10e9 /L	-
Alanine aminotransferase increased	>ULN - 3.0 x ULN if baseline was normal; 1.5 - 3.0 x baseline if baseline was abnormal	>3.0 - 5.0 x ULN if baseline was normal; >3.0 - 5.0 x baseline if baseline was abnormal	>5.0 - 20.0 x ULN if baseline was normal; >5.0 - 20.0 x baseline if baseline was abnormal	>20.0 x ULN if baseline was normal; >20.0 x baseline if baseline was abnormal	
Aspartate aminotransferase increased	>ULN - 3.0 x ULN if baseline was normal; 1.5 - 3.0 x baseline if baseline was abnormal	>3.0 - 5.0 x ULN if baseline was normal; >3.0 - 5.0 x baseline if baseline was abnormal	>5.0 - 20.0 x ULN if baseline was normal; >5.0 - 20.0 x baseline if baseline was abnormal	>20.0 x ULN if baseline was normal; >20.0 x baseline if baseline was abnormal	
Blood bilirubin increased	>ULN - 1.5 x ULN if baseline was normal; > 1.0 - 1.5 x baseline if baseline was abnormal	>1.5 - 3.0 x ULN if baseline was normal; >1.5 - 3.0 x baseline if baseline was abnormal	>3.0 - 10.0 x ULN if baseline was normal; >3.0 - 10.0 x baseline if baseline was abnormal	>10.0 x ULN if baseline was normal; >10.0 x baseline if baseline was abnormal	
Creatinine increased*	>ULN - 1.5 x ULN	>1.5 - 3.0 x baseline; >1.5 - 3.0 x ULN	>3.0 x baseline; >3.0 - 6.0 x ULN	>6.0 x ULN	

\*The reference range for Grade 2 and Grade 3, that includes the baseline value, is not applicable if the baseline value is abnormal.

## 11.5 List of SRC outputs

Efficacy Output:

- Mean and mean % change from baseline in SALT by visit

Safety Outputs:

### TEAE

- Overall summary of TEAE
- Summary of TEAEs by SOC and PT
- Summary of Serious TEAEs by SOC and PT
- Summary of TEAEs with CTCAE grade 3 or higher by PT
- Summary of treatment related TEAEs by SOC and PT

### Lab values

- Number (n) and percentage (%) of participants with CTCAE grade for key hematology parameters (WBC, neutrophils, lymphocytes, eosinophils, platelet, and hemoglobin)
- Number (n) and percentage (%) of participants with CTCAE grade for key serum chemistry parameters (ALT, AST, serum creatinine, and bilirubin)

### Vital signs

- Notable findings in vital signs

### ECG

- Notable findings in ECG
